Number of clinicians and family members present	Presence of others in the room in addition to patient and surgeon
Any part of the transcript in a language other than English	Presence of any language other than English spoken by any person present during the audio recording
Audio-recording and transcript captured full conversation	Presence of gaps or content that appears to be missing from the surgeon's visit with the patient, pauses, lack of greetings or goodbyes
Discussion included any consideration of operative treatment/surgery and, if yes, was this a high-risk procedure or operation	Presence of a discussion about any major operative procedure
Mention that surgery had been discussed with this patient and this surgeon or another surgeon before	Reference to previous discussions or interactions with another surgeon prior
Type of indication	Presence of a discussion about a vascular or oncologic problem
Additional specific topics covered	Goals of treatment as stated by surgeon, patient goals, advance care planning, and surgeon's ambivalence about surgical intervention

Data from the “Measure Yourself Concerns and Well-being” (MYCaW) instrument will be coded using a codebook developed by the research team. The coding scheme was developed in the following way: each concern is given a primary code that best captures the essence of the concern. Up to 4 secondary codes can also be applied to each concern to capture additional themes raised. Two coders will independently code each concern, blinded to treatment arm status and site. Three study team members will meet to consensus code and resolve all discrepancies.

Data on regrets expressed by patients and family members during the T3 survey will be coded by 2 coders, blinded to intervention arm, based on a previously developed coding scheme.⁴¹ Data from this survey item will be coded for the presence or absence of regret and, when regrets are present, will be coded with one or more topic areas.

Per-Protocol Analysis of Primary Outcomes

General Analysis Plan

As described in our PCORI funded proposal, our primary analysis will compare the effectiveness of the QPL intervention relative to usual care on patient engagement for aim 1 and psychological wellbeing for aim 2. We will use an intention to treat (ITT) analysis using all available data from participants based on group assignment.

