MYCaW: The difference in the rating of the primary concern between T1 and T2, regardless of the categorization of this concern, as reported by the patient will be treated as a continuous outcome and analyzed with a linear mixed effect model. We will accommodate the longitudinal nature of the data with a patient level random effect. Analyses will be based on a treatment difference relative to T1 at T2 in a random effects model with: a treatment difference at T1, a time (0/1) variable indicating either T1 versus T2, an intervention-by-time interaction representing the treatment difference, and a random effect at the patient level.

We will use linear mixed effects models for continuous responses (MYCaW), logistic random effects models for binary responses (regret).

Further analysis of primary endpoints generated prior to un-blinding

Updated analysis plan and modified power analysis

Rationale: Prior to unblinding (looking at treatment group assignment) and after commencement of data coding in preparation for analysis, the research team became aware of 2 issues that prompted modification

of our per-protocol analysis plan. First, reports from our DSMB demonstrate that PEPPi-5 for this cohort of patients and family members has remarkable ceiling effects (for 333 enrolled participants, mean score 21.4, IQR 20-24, scale range: 0 - 25). Thus, even if we demonstrate a significant difference it would be clinically meaningless. Second, the variability in self-reported concerns using the open-ended MYCaW instrument for patients and family members in this study is enormous. For example, some patients note concerns about parking or how the surgeon communicated with them, whereas others note concerns about removing their cancer or how they will feel after surgery. This makes it difficult to compare concerns between the entirety of the two groups and suggests a need for stratification of these outcomes in relation to the patient's clinical course, specifically whether there was a decision to have surgery. As surgical treatment is a post-randomization variable, such analysis is not appropriate for a primary outcome. In response to these 2 concerns, we recalculated our power analysis without the PEPPi-5 endpoint in aim 1 and without the MYCaW endpoint in aim 2 as these were no longer valid primary outcomes.

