- Number of EXPECTATION questions asked by patients and family members (0, 1, 2+)
- Number of ADVANCE DIRECTIVES questions asked by patients and family members (0, 1+)

-Number of RISKS questions asked by patients and family members (0, 1, 2+)

Denote each question type with [Q-type], where type is either Options, Expectation, Advance Directives, or Risks. [Q-Advance Directives] is a binary variable, the other three types are three-category ordinal variables. Accordingly, a logistic random effects model will be used to analyze [Q-Advance Directives], while ordinal logistic random effects models will be used for analyzing the other three types.

For Aim 2, there is no change to the modeling approach for regret: we will use a logistic random effects model. We will use an intention to treat analysis using all available data from participants based on group assignment. We will use a logistic random effects model with a treatment dummy variable, surgeon random effect and site-by-time dummy variables to control site-specific secular trends.

Additional considerations: Aim-1 question asking

After performing the ITT analysis, we will restrict the analysis by removing the dyads (patient and family member) where major surgery was not discussed or the patient did not have a vascular or oncologic problem. This is based on the T0 transcript of the conversation with the surgeon, which confirms whether the patient discussed surgery with the surgeon and had a vascular or oncologic problem. Specifically, we will use the subgroup analysis document, coded by the primary coder and confirmed in group consensus, to identify enrolled patients for whom surgical treatment was not discussed, or on evaluation after enrollment, the patient did not make entry criteria to be in the study, specifically, the patient did not have a diagnosis of cancer or vascular disease.

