For all secondary outcomes after completing the ITT analysis, we will perform a restricted analysis as described in the additional considerations section above. Specifically, we will restrict the analysis by removing the dyads (patient and family member) based on the T0 transcript of the conversation with the surgeon, which confirms whether the patient discussed surgery with the surgeon and had a vascular or oncologic problem. Next, we will further restrict the analysis based on penetrance of the intervention based on the criteria described above.

Additional important outcomes

Family member presence: We plan to compare the proportion of patients who are accompanied by a family member or “like family” friend to the visit with the surgeon between the intervention and control group as receipt of the QPL prior to a visit with a surgeon may prompt patients to bring a family member with them to the consultation visit for additional decision-making support. This binary outcome variable (yes/no family member present) will be ascertained from the T0 transcript which clearly notes number of family members/friends. Family members do not need to be enrolled in the study to be counted as present. We will use ITT analysis as well as a restricted analysis (as described above) to analyze this outcome.

Consult duration: We will compare the median consult length at T0 between groups. This is not an effectiveness outcome but rather information that clinicians and patients might want to know in considering use of the intervention in their clinic. We will also compare the median consult length within surgeon (pre/post) to account for fairly wide variation in surgeon routine (some surgeons clearly spend

45-60 minutes with patients whereas others spend 7-15 minutes with patients). Given that surgeons will have been assigned randomly to intervention wave the incidence of pre/post measurements will not be evenly distributed and may be too variable to determine real differences.

Exploratory analyses

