surgery, for example an aneurysm that does not meet size guidelines for operative repair, will be excluded based on chart review or previsit determination by the surgeon.

Recruitment

At each study site, all eligible surgeons will receive an invitation via e-mail by the site principal investigator. Surgeons who do not opt out will be chosen first based on surgical subspecialty to capture variability in high-risk procedures and second by random selection of surgeons within a given subspecialty. Surgeons will not receive incentives for participation. We aim to enrol 40 surgeons in total, with the number of surgeons selected to be approximately proportional to the surgical volume at each site.

Study staff will review the clinic schedule of each enrolled surgeon and identify eligible patients based on chart review and clinic intake forms. On the day of clinic, study staff will meet with interested patients and family

members to explain the study and obtain informed consent prior to the conversation with the surgeon. Patients and family members will receive financial incentives valued at \$55 for participation. To avoid over-representation of any one surgeon, after each surgeon has two patients enrolled within the 4-month wave, recruitment will cease for that surgeon's patients until the next wave begins. We aim to enrol a total of 480 patients across all five sites, with 12 patients per surgeon.

We will use stratified purposeful sampling to identify a subset of enrolled patients (and family members, if applicable) who underwent surgery and experienced a serious postoperative complication, as determined by chart review. Serious complications include prolonged hospitalisation (more than 8 days postoperatively), prolonged length of stay in intensive care (greater than 3 days), prolonged mechanical ventilation, myocardial

Table 2 Primary and secondary outcome measures (items in bold are primary outcomes)

Construct	Specific measure	Source	Timing
Aim 1: Patient engagement			
Engagement in decision making	
 ▶ Number and type of questions using a predefined coding scheme ▶ OPTION 	Audio recording	Clinic visit
Self-efficacy in patient-physician interactions	
 ▶ PEPPI-5 (perceived efficacy) ▶ HCCQ (autonomy support) 	Patient and family member	First questionnaire
Aim 2: Psychological well-being and treatment received			

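### The supportive restricted analyses drop visits where surgery was not discussed, a post-randomization variable that the QPL could affect, without labelling it as such

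*Combined protocol and SAP*

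**What the plan says.** The rule stands in the SAP under Additional considerations: Aim-1 question asking. It comes second in order: "After performing the ITT analysis, we will restrict the analysis". Two kinds of dyad are removed: those with no vascular or oncologic problem, and those met by "removing the dyads (patient and family member) where major surgery was not discussed". The source is stated: "This is based on the T0 transcript of the conversation with the surgeon, which confirms whether the patient discussed surgery with the surgeon". Table 4 of the SAP lists the matching coded item: "Discussion included any consideration of operative treatment/surgery and, if yes, was this a high-risk procedure or operation".

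The rule then spreads:

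- The penetrance analysis, in the same section, restricts this set further.
- The closing paragraph on secondary outcomes says: "For all secondary outcomes after completing the ITT analysis, we will perform a restricted analysis as described in the additional considerations section above". It repeats the source: "we will restrict the analysis by removing the dyads (patient and family member) based on the T0 transcript".
- Family member presence, under Additional important outcomes, also gets a restricted analysis.

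On restricting by what happens after allocation, the SAP speaks elsewhere. The updated analysis plan says of stratifying MYCaW by the decision to have surgery: "As surgical treatment is a post-randomization variable, such analysis is not appropriate for a primary outcome". The section on the stratified MYCaW analysis then openly calls its stratifier post-randomization. The restricted-analysis paragraphs carry no such label and do not ask for exclusions by arm.

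**The concern.** The appended published protocol (Intervention) has the QPL and the surgeon's letter mailed before the appointment. T0 is the conversation they are meant to change. One transcript then supplies both the filter (was major surgery discussed?) and the outcomes (question counts, OPTION 5).

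There are plausible routes from the QPL to the filter. Its first block of prompts is about whether to have surgery at all. Surgeons know their allocation and are reminded every two weeks to support use of the list. Under the coding manual, an OPTIONS question about alternatives to surgery is a scored outcome, and the same question can put surgery on the record. For that question type, filter and outcome partly overlap.

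If the QPL changes which visits pass the filter, the visits kept in the two arms are no longer comparable by design, even when the QPL has no effect on any patient's questions. The SAP describes the filter next to failure of entry criteria, so the restricted estimate could be taken as an effect in properly eligible patients when part of it is selection.

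**Working it through.** The plan states no figure for this restriction, so there is nothing to reproduce. The calculation below shows how large the bias could be.

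**Inputs.** All are assumptions, because the documents give no rates for this filter. The outcome is simplified to none versus at least one question of a given type. Clustering and site-by-time terms are ignored.

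- *A* = share of visits that discuss surgery in either arm: 0.80 or 0.90.
- *c* = further share that discuss surgery only because of the QPL: 0.03, 0.05 or 0.10.
- Asking rate in the always-discussed visits: 0.40 in both arms.
- *r* = asking rate in the added visits: 0.05 to 0.70, the same with or without the QPL. There is thus no true effect on any patient's questions.

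**Formula.** The restricted control arm keeps only the always-discussed visits, so its rate is 0.40. The restricted intervention rate is (A × 0.40 + c × r) / (A + c). The restricted odds ratio is the odds of that rate divided by the odds of 0.40, which are 0.40/0.60 = 0.667.

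**Worked example.** With A = 0.80, c = 0.05 and r = 0.05, the rate is (0.320 + 0.0025)/0.85 = 0.379. The odds are 0.379/0.621 = 0.611, and the odds ratio is 0.611/0.667 = 0.917. With r = 0.70 the rate is 0.355/0.85 = 0.418 and the odds ratio 1.076.

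| A | c | OR at r = 0.05 | OR at r = 0.70 |
|---|---|---|---|
| 0.80 | 0.03 | 0.948 | 1.046 |
| 0.80 | 0.05 | 0.917 | 1.076 |
| 0.80 | 0.10 | 0.848 | 1.147 |
| 0.90 | 0.03 | 0.954 | 1.041 |
| 0.90 | 0.05 | 0.926 | 1.068 |
| 0.90 | 0.10 | 0.862 | 1.132 |
| either | 0 | 1 | 1 |

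The direction depends on whether the added visits hold fewer or more questions of that type than the rest.

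**A second setting**, tied to the SAP's assumption that 65% of control patients fall in the zero category. Take 35% asking in both arms and 10% asking in visits without surgical discussion. The restricted rate is (0.35 − n × 0.10)/(1 − n), where n is the share of visits excluded.

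- n = 15% control, 10% intervention: 0.335/0.85 = 0.394 against 0.340/0.90 = 0.378, OR 0.93.
- n = 20% control, 10% intervention: 0.330/0.80 = 0.4125 against 0.3778, OR 0.8647, or 0.86.

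Both fall below 1 only because the excluded visits were given a low asking rate. They lie inside the ranges above.

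**Scale.** The SAP's power calculation uses an odds ratio of 1.3. The most extreme value in the table is ln 0.848 / ln 1.3 = −0.165/0.262, about 0.63 of that effect in size. The ratio is no firmer than its inputs.

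**The case against.** The case on the other side is strong on several points.

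- **The SAP does not breach its own principle.** A reader might infer that it bars post-randomization restriction for MYCaW and then applies it to the Aim 1 primaries. The documents do not support this. The bar concerns a primary outcome, and the primary analysis of the Aim 1 endpoints is ITT. The restriction comes afterwards, just as the stratified MYCaW analysis is kept as a non-primary one. This stands in full.
- **The key link is not measured.** No passage shows that the QPL changes whether surgery is discussed. Every enrolled patient sees a surgeon about a new surgical problem, and the first part of the Table 4 item (any consideration of surgery) is a low threshold. The QPL development paper reports a pilot patient who realised from the QPL that surgery was possible, but this does not show that the consultation's content changed. Nor does any passage report that visits without surgical discussion hold fewer scored questions, so a bias toward a smaller effect cannot be claimed.
- **Coding is blinded and confirmed by consensus.** This limits coder bias. It does not prevent selection, because the conversation itself may differ by arm.
- **Re-applying pre-visit eligibility would achieve little.** Under Participants, the published protocol says patients without a surgically treatable problem "will be excluded based on chart review or previsit determination by the surgeon". Enrolled patients have already passed that screen, and the SAP's restriction aims to catch what it missed. A full blinded re-adjudication of charts would be new work.

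These points limit the size and certainty of the concern. They do not change the fact that the filter is observed after the intervention, in the same conversation as the outcomes, and is not labelled so.

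**Conclusion.** The concern holds for the supportive restricted analyses: the Aim 1 question types, all secondary outcomes, and the penetrance analysis built on the same set. The criterion that causes it is surgery not discussed. The other criterion, no vascular or oncologic problem, is close to a baseline fact.

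With no true effect, the bias runs from an odds ratio of about 0.92 to 1.08 for a 5-point shift in which visits discuss surgery, and about 0.85 to 1.15 for a 10-point shift. It is zero if there is no shift. These figures rest on assumed rates and a simplified binary model, so they show what is possible and do not predict a result.

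A reader might go further and infer that the main trial result is compromised. It is not: the ITT analysis uses all available data by assigned group and is untouched. What is missing is the post-randomization label that the SAP gives its MYCaW stratifier, and a way to see whether exclusions differ by arm.

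**What to change.** In the SAP's Aim 1 considerations, and in the paragraph that carries the restriction to the secondary outcomes:

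1. Define the inferential restricted set only by the absence of a vascular or oncologic problem. Take this from the patient's presenting problem, which Table 3 of the published protocol already lists as abstracted by chart review, in place of the T0 transcript. Build the penetrance analysis on this set.
2. Keep the surgery-not-discussed restriction as a descriptive analysis, and label it post-randomization in the same terms as the MYCaW stratifier.
3. Tabulate exclusions by arm and by reason. Unequal rates would warn of selection. Equal rates would be reassuring but not proof, since the kinds of visit excluded could still differ.

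The cost is SAP wording, one table and use of a variable already collected. The downside is that some visits with no surgical discussion stay in the restricted set, which may dilute its estimate slightly.

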Risks & Complications	Seeks to understand what could go wrong, bad outcomes or hazards of surgery.	"As far as the location of the tumor that remains in those veins...is anything at risk as far as... blood flow function of any of those parts?"
Logistical & Technical	Seeks to understand the technical details about how surgical treatment is performed and how to coordinate personal needs associated with treatment.	"How long does the surgery take?"
Other	Queries regarding things external to the diagnosis, decision-making or treatment.	"How many grandkids do you have?"
Question categories in bold are primary outcomes .		

Table 3: Intraclass correlation between coders for question category coding of patient and family members during T₀ surgical consult		
Category	ICC 1	ICC 2
Options	0.45	0.76
Expectations	0.95	0.83
Risks & Complications	0.79	0.87
Logistical & Technical	0.93	0.92
Advance Directives	Not analyzed	Not analyzed
Other	Not analyzed	Not analyzed

Each transcript will be coded by one coder. A full codebook is provided in the Appendix. Audio recordings will be transcribed with all identifying information removed including names, dates and locations. Prior to coding, every transcript will have a thorough quality assurance check by a member of the study team to ensure the transcript fully captured what occurred during the T₀ visit, and that all questions were appropriately transcribed. Prior to categorizing each question, questions asked by patients

or family members will be identified by a Microsoft Visual Basic program, which will generate a coding sheet containing all questions asked by patients and family members during the T0 surgeon visit.

Each transcript will also be coded based on the OPTION 5 instrument, a measure of observer measured shared decision making⁴⁰ as designed by Elwyn (see Appendix). Satisfactory acceptable intraclass correlation for this measurement was difficult to attain so each transcript will be OPTION 5 scored by 2 coders and then consensus coded during group coding sessions.

Each transcript will be coded for other variables, as shown in Table 4. This coding will be done by a single coder and then consensus coded as part of group coding sessions.

Table 4: Additional variables derived from the transcribed audio recordings	
Variable	Coding details
Length of audio file	Duration of the transcribed audio recording

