Next, we will further restrict the analysis based on penetrance of the intervention. We will identify patients in the intervention group with a clear signal that they received the QPL prior to the visit with the surgeon. This will be identified by one or more of the following criteria 1) clear presence or use of the QPL in the audio recorded conversation with the surgeon (noted in less than 20 transcripts), 2) coder identification of something that could be the QPL used during the conversation with the surgeon (coder marked this as unsure), 3) affirmative answer on the T1 survey from the patient or family member that they received something that might be the QPL from the surgeon prior to clinic visit (using a sensitivity analysis based on the certainty around receipt of the QPL within the response to this question), 4) a maybe answer on the T1 survey, 5) notes from the research coordinator that the patient was seen in clinic with a QPL.

Additional analysis will adjust for age and comorbidity. We will also evaluate a composite endpoint of all 4 question types where each of the 4 question types is categorized as binary and the composite score is ordinal (0, 1, 2, 3, 4) such that 4 signifies that a question of each type has been asked.

Additional considerations: Aim-2 regret

We will first consider regret as a binary outcome and then do additional analysis with regret considering this as a categorical variable with 0 = neither patient or family member has regret, 1 = either patient or family member has regret, 2 = both patient and family member have regret.

Stratified Analysis: Aim-2 MYCaW

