 - After you have coded the entire transcript, use "Ctrl-F" to skip from question mark to question mark to double check that you haven't missed any questions and have labeled speakers correctly
- If a question is within quotation marks (for example, if a patient is quoting someone else's question), that counts as a question and should be coded for topic area just like any other question
 - Example: "And then others go, 'what are you crazy, you're going to get it fixed?... Why would you even think about getting it fixed?'"
 - This counts as two questions
 - 1) "What are you crazy, you're going to get it fixed?"
 - 2) "...Why would you even think about getting it fixed?"

*What **DOES NOT** count as a question for this study?*

- Do not code questions asked by the surgeon or another member of the clinical care team
- Do not code questions asked by patients or family members when the surgeon is not in the room
- Do not code anything that appears question-like but lacks a question mark at the end. These utterances do not count. The following are NOT questions as they lack question marks:
 - "Is there a possibility of me getting a recording from this, because..."
 - "So in my case, you have to remove it."
 - "I don't know what the plasma is."
- Question marks that appear inside square brackets [?] refer to transcriptionist questions (usually about content that is inaudible or medical jargon) and do not count.
 - For example, the following do not count as questions:
 - [inaudible?]

- [Lovastatin?]
 - “He’s teaching me [lots? 2:49]”
- However, question marks that appear *outside* a square bracket do count as questions.
Example: “Do I have to go back to [REHAB NAME]?”

What about multi-part questions where there are 2 or more questions included in the same section of text? How many questions does this count as?

- The number of questions is based solely on the number of question marks
 - For example, this is 5 questions, each entered as its own row in the coding sheet: “But, I mean, does he make an appointment for this surgery in October? I mean, how far out are you looking? Is it really full? I mean, do you ask for that now, the appointment? Do you . . . cancel?”
- Words like “So?” or “Right?” at the end of another question count as unique questions
 - This is two questions: “So the chances of it opening up again are low? Right?”
 - See Step 3 on how to code the topic area for tag-on words like this

What if the speaker is interrupted while asking a question?

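### The supplementary penetrance analysis selects intervention patients partly on the recorded visit that supplies the question counts, so its contrast can lean toward benefit with no true effect

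*Combined protocol and SAP*

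**What the plan says.** The section on additional considerations for Aim 1 question asking sets out two restrictions in sequence. The first is an eligibility step applied to both arms: "After performing the ITT analysis, we will restrict the analysis by removing the dyads (patient and family member) where major surgery was not discussed", or where the patient had no vascular or oncologic problem. The second is the penetrance step: "We will identify patients in the intervention group with a clear signal that they received the QPL prior to the visit with the surgeon".

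Meeting any one of five criteria is enough:

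- **Criterion 1:** "clear presence or use of the QPL in the audio recorded conversation with the surgeon (noted in less than 20 transcripts").
- **Criterion 2:** a coder's unsure identification of something in the conversation that could be the QPL.
- **Criterion 3:** "affirmative answer on the T1 survey from the patient or family member that they received something that might be the QPL".
- **Criterion 4:** a 'maybe' on the same survey.
- **Criterion 5:** "notes from the research coordinator that the patient was seen in clinic with a QPL".

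The section plans a sensitivity analysis on the certainty of the T1 answer, and a further analysis adjusted for age and comorbidity. It states no filter for controls and does not name the comparator.

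The Aim 1 counts come from the same T0 recording. Under Data coding, a program screens the transcript, "which will generate a coding sheet containing all questions asked by patients and family members during the T0 surgeon visit". T1 takes place 24 to 48 hours after the visit (notes to Table 1), and the receipt question is its last item (Blinding).

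The closing paragraph on secondary outcomes reuses the step for all of them: "Next, we will further restrict the analysis based on penetrance of the intervention based on the criteria described above".

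**The concern.** The stated aim is to find patients who received the list before the visit. Criteria 1 and 2 instead detect its presence or use during the visit, which is when the outcome is measured. A patient who reads a listed question aloud can be flagged as a recipient and counted as an asker by the same utterance. A patient who received the list but never showed, mentioned or used it cannot qualify by this route. Criteria 3 and 4 are also collected after the visit, so more engaged patients may be more likely to recall the mailing.

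Selection therefore happens after randomisation, in one arm, and can depend on the outcome. If the receipt signals track asking, the retained intervention patients contain too many askers and the comparison favours the QPL even when it does nothing. Neither planned extra analysis deals with this: the T1-certainty analysis leaves criteria 1 and 2 in place, and age and comorbidity do not capture behaviour at the visit.

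What is at stake is how the penetrance-restricted results may be read, since they could be taken as the effect in patients who actually received the intervention.

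**Working it through.** The plan gives no sample size, power or error rate for the penetrance analysis, so there is no figure to reproduce. The check asks what odds ratio the filter would produce with no true effect.

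**Inputs from the documents.** From the updated power section: 221 intervention patients, and 65% of controls asking no question of a given type (the plan's worst case), so 35% ask. Criterion 1 gives fewer than 20 transcripts, so at most 19 flags. These figures precede the eligibility step.

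**Not in the documents.** The criterion 2 count, the share kept by other routes (*o*), and how strongly flags or recall track asking. These are assumptions, shown as ranges.

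**Formula.** Let *ra* and *rn* be the proportions of askers and non-askers retained. With asking probability *p* in both arms, the odds of asking among retained intervention patients are *p·ra* / [(1−*p*)·*rn*], against *p*/(1−*p*) in controls. The null odds ratio for any versus no question is therefore *ra/rn*, where each *r* = *o* + (1−*o*)·*f* and *f* is the proportion flagged in the recording. Askers number 0.35 × 221 = 77.35 and non-askers 143.65.

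**Other routes unrelated to asking, 19 flags:**

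| Link between flag and asking | *f* askers | *f* non-askers | *o* = 0.3 | *o* = 0.5 | *o* = 0.7 |
|---|---|---|---|---|---|
| None | 0.086 | 0.086 | 1.00 | 1.00 | 1.00 |
| Askers twice as likely | 0.127 | 0.064 | 1.13 | 1.06 | 1.03 |
| Every flag an asker (extreme) | 0.246 | 0 | 1.57 | 1.25 | 1.11 |

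For row two, *f* in non-askers is 19/(143.65 + 2 × 77.35) = 0.0637. For row three, *f* in askers is 19/77.35 = 0.2456, so at *o* = 0.5 the ratio is 1 + 0.2456 × 0.5/0.5 = 1.25.

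**Sensitivity at *o* = 0.5.**
- If 50% ask, the extreme case falls to 1 + 19/110.5 = 1.17.
- If the eligibility step removed 20% of patients and all 19 flags stayed (assumption), it rises to 1 + 19/61.88 = 1.31.
- With 38 flags from criteria 1 and 2 together (assumption), the ratio is 1.11 if askers are twice as likely to be flagged and 1.49 in the extreme case.

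**Recall that tracks asking.** Suppose other routes keep 70% of askers and 50% of non-askers (assumption).
- Flags unrelated to asking: (0.7 + 0.3 × 0.086)/(0.5 + 0.5 × 0.086) = 0.7258/0.5430 = 1.34.
- Askers twice as likely to be flagged: 0.738/0.532 = 1.39.
- Criteria 1 and 2 dropped: 0.70/0.50 = 1.40.
- Every flag an asker: 0.774/0.50 = 1.55, so only with a strong link such as this does dropping the criteria help.

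**Three-category outcomes.** With an assumed control split of 65/20/15%, and retention depending only on any versus none, a proportional-odds fit gives a common odds ratio of 1.23 where the binary figure is 1.25, and 1.53 where it is 1.57. Comparison with the planned odds ratio of 1.3 is therefore approximate.

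**False-positive rate.** A stepped-wedge power model with the planned rollout gave 82.4% and 93.2% power at an intraclass correlation (ICC) of 0.05 and alpha 0.025, matching the published protocol's 82% and 93%. Null trials (1,000 per setting, linear mixed-model approximation) were then simulated on the same design. With every flag an asker and *o* = 0.4, the chance of a false benefit at two-sided 0.0125 was 3.4% (ICC 0.30) to 5.7% (ICC 0.05), against a nominal 0.6% per side. With no recording flags and the same random thinning it was 0.7%. In this model the inflation comes from selecting on the visit and not from the smaller sample.

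**The case against.** The strongest reply is that this is a supplementary analysis. It follows the ITT analysis and carries no alpha, power or decision rule. The team also knows the principle: when dropping MYCaW as a primary endpoint it rejects stratifying a primary outcome on surgical treatment because that is a post-randomisation variable, and it names the MYCaW stratifier as one. All of this stands, and it limits the point to interpretation and labelling.

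Second, the bias may be small. That also stands. Criterion 1 covers presence as well as use, so a brochure merely mentioned would qualify, and the extreme row needs every flagged patient to have asked a question of the particular type analysed. A reader might infer from 1.57 that a spurious effect larger than the planned 1.3 is to be expected; the documents do not support that.

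Third, a reader might infer that replacing the definition with the patient's T1 answer would cure the problem. It would not. The published protocol's Table 3 item asks only about information received in the mail, the answer still follows the visit, and under the recall pattern above dropping the recording criteria moves the null odds ratio from 1.34 to 1.40. Nor can a matching receipt filter be imposed on controls, who are not mailed the QPL. Being one-sided is inherent in any receipt filter here.

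What the reply does not answer is that two criteria overlap with the outcome's own source, that no planned analysis shows results without them, and that the penetrance step lacks even the description given to the MYCaW stratification.

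**Conclusion.** The concern holds for the supplementary penetrance analysis only. As written, its selection is post-randomisation and can depend on the outcome, and for question counts it leans toward benefit if the receipt signals track asking.

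The size is not established. On 19 flags, 35% asking and other routes unrelated to asking, the null odds ratio runs from 1.0 to 1.13 with no or moderate linkage, and from 1.11 to 1.57 only in the extreme case. Recall that tracks asking could give about 1.34 to 1.40 in the assumed scenario, with or without criteria 1 and 2. Retention, the criterion 2 count and the linkage are all assumptions.

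Three stronger readings are not supported. The primary ITT analysis, which carries the alpha and power, is untouched. For the secondary outcomes that reuse the step, the direction of bias is not established. For family presence, the reference to a restricted analysis could mean the eligibility step alone.

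**What to change.** 1. Report the penetrance-restricted results with and without criteria 1 and 2, and report QPL use heard in the recording descriptively.
2. Also show results using the patient's own T1 answer alone, with 'maybe' counted both as receipt and as non-receipt. Do not claim that this removes the bias or always reduces it.
3. State that the comparator is the controls left after the eligibility step. Label every penetrance-restricted result, for Aim 1 and for the secondary outcomes, as exploratory and not protected by randomisation, in line with the plan's naming of the MYCaW stratifier as post-randomisation.

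The cost is SAP wording and a few extra model runs on data already collected (the plan reports 97% of patients completing T1). Without criteria 1 and 2 the restricted set is smaller and its estimate less precise: criterion 1 accounts for at most 19 of 221 patients (8.6%), and the loss from criterion 2 cannot be read from the documents. A complier-average analysis using the randomised crossover schedule as instrument is optional and not part of the required change.
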